8.0 DATA ANALYSIS PLAN

A statistical analysis is not proposed. For this study, the Safety and Effectiveness assessment will be descriptive with no statistical endpoints. The results will be examined and analyzed and used as a basis for determining the nature of future studies.

8.1 Safety

All adverse events will be recorded and categorized according to severity, relationship to procedure and relationship to device. Any subject who receives at least one sonication will be considered Intent to Treat (ITT) for safety assessments. All AEs will be assessed for their relationship to the study device or procedure. Standard Code of Federal Regulation definitions for Serious Adverse Events (SAEs) and Unanticipated Adverse Device Effects (UADEs) will be used in assessment of AEs.

8.2 Efficacy

The primary efficacy outcome is the change in worst NPRS score from baseline to 3 months compared between medial thalamotomy and sham procedures with no change or increase in baseline pain medications. A mean change of 2 points has been shown to be clinically significant.⁹⁹ Responder analysis (e.g. number of subjects who have 3-point or better improvement in worst NPRS pain score at 1 and 3 months) will also be performed. Data analyses will also be performed on all PROMIS measures and other subject-reported measures, including PET.

If there is a significant symptomatic pain medication change following MRgFUS treatment, the subject's data will not be used in the Efficacy analysis but the aspects of their procedure will still be included in the Safety analysis.

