5.2 Inclusion Criteria

1. Men and women, between 18 and 75 years, inclusive
2. Subjects who are able and willing to give consent and able to attend all study visits
3. Severe chronic, trigeminal neuropathic pain of ≥ 6 months duration.
4. Severity is defined as: Worst NPRS score of ≥ 5 out of 10 at current visit and the subject reports having a similar level of pain for at least the past two months.
5. Pain is medication-refractory to adequate trials of at least 3 prescription medications commonly used for symptomatic relief of neuropathic pain with current adjunctive use of at least one medication. An adequate medication trial is defined as a therapeutic dose of each medication without sufficient effect.
6. Pain is treatment-resistant to at least one interventional therapies including injections, procedures, neuromodulation, and surgery. The interventions trialed depend on the disease and are more specifically defined below:
 - Trigeminal neuropathic pain: failed peripheral injection, percutaneous RF ablation, transcutaneous stimulation, peripheral nerve stimulation, caudalis DREZ lesioning, trigeminal tractotomy, motor cortex stimulation, intraventricular or intrathecal medication infusions, or deep brain stimulation
 - Trigeminal deafferentation pain: pain has resulted from failed trigeminal procedures including percutaneous RF rhizotomy, percutaneous chemical rhizotomy, percutaneous balloon compression rhizotomy, stereotactic radiosurgery, microvascular decompression, or intracranial partial sensory rhizotomy
 - Postherpetic neuralgia of the trigeminal nerve: failed peripheral injection, percutaneous RF ablation, transcutaneous stimulation, peripheral nerve stimulation, caudalis DREZ lesioning, trigeminal tractotomy, motor cortex stimulation, intraventricular or intrathecal medication infusions, or deep brain stimulation
7. Central lateral nucleus of thalamus can be targeted by the ExAblate device. The CL region of the thalamus must be apparent on MRI such that indirect targeting can be performed by measurement from a line connecting the anterior and posterior commissures of the brain.
8. Able to communicate sensations during the focused ultrasound treatment

9. Stable prescribed doses of all symptomatic pain medications for 30 days prior to study entry and for the duration of the 3-month blinded phase of the study.
- 10.

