6.7 Follow-up

Subject follow-up will be completed at Day 1, Day 7, Month 1, and Month 3 for all subjects who underwent CL lesioning/ablation using ExAblate system. Subject follow-up will be similar for those who underwent sham treatment. At 3 months, subjects who had sham treatment will be unblinded and offered MRgFUS.

Subjects will be evaluated at all follow-up visits for general health, neurological changes and efficacy measurements as well as for device/procedure related adverse events that may have occurred during the follow-up period. Medication regimen and PRN usage will be recorded at each follow-up along with the following assessments:

6.7.1 Day 1

- Evaluation of general health and neurological changes
- NPRS (Worst pain in 24 hrs)
- PROMIS
- Assess patient blind
- Assess safety and update adverse events as needed
- Review medications and record any changes
- MRI

6.7.2 Day 7

- Evaluation of general health and neurological changes
- NPRS (Worst pain in 24 hrs)
- PROMIS
- PGIC
- Assess patient blind
- Assess safety and update adverse events as needed
- Review medications and record any changes
- MRI

6.7.3 Month 1

- Evaluation of general health and neurological changes
- NPRS (Worst pain in 24 hrs)
- PROMIS
- PGIC
- Assess patient blind
- Assess safety and update adverse events as needed
- Review medications and record any changes
- MRI

6.7.4 Month 3

- Evaluation of general health and neurological changes
- NPRS (Worst pain in 24 hrs)
- PROMIS
- PGIC
- Assess patient blind
- Neuropsychological Pain Assessment
- GAD-7
- PHQ-9
- PCS
- BBHI-2
- MRI

- Dynamic FDG PET
- Assess safety and update adverse events as needed
- Review medications and record any changes
- Evaluation by a pain management physician

All pre-treatment and post treatment MR images will be de-personified (i.e.: subject identifiers made anonymous), archived and sent to InSightec. These analyses will also include full radiological assessments from baseline through all follow up visits.

In this study, subjects who use alternative treatments (not including medication change) during the 3-month follow-up period will be exited from the study, after completing required study examinations. The reason(s) for study exit will be noted on the Case Report Forms.

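### Section 8.2 removes subjects from the efficacy analysis for a pain medication change after randomisation, which can distort the thalamotomy-versus-sham comparison of worst NPRS

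*Protocol*

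**What the plan says.** Section 8.2 makes the change in worst NPRS from baseline to 3 months, thalamotomy against sham, the primary efficacy outcome, and qualifies it: "with no change or increase in baseline pain medications". It adds a benchmark: "A mean change of 2 points has been shown to be clinically significant". A separate paragraph gives the deletion rule. Its trigger is "If there is a significant symptomatic pain medication change following MRgFUS treatment", and its consequence is that the subject's "data will not be used in the Efficacy analysis but the aspects of their procedure will still be included in the Safety analysis".

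Other parts of the protocol bear on this:

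- Section 6.4 places randomisation immediately before the first sonication, so anything that follows treatment is post-randomisation.
- Section 5.2, criterion 9, requires "Stable prescribed doses of all symptomatic pain medications for 30 days prior to study entry and for the duration of the 3-month blinded phase".
- Section 6.7 states that "Medication regimen and PRN usage will be recorded at each follow-up", and that "subjects who use alternative treatments (not including medication change) during the 3-month follow-up period will be exited from the study". A medication change is therefore expressly not a reason for exit.
- Section 8.1 defines an intent-to-treat set for safety only. No efficacy summary that keeps every randomised subject is described.
- Section 8.0 makes the assessment descriptive, with results to be "used as a basis for determining the nature of future studies".

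**The concern.** Randomisation makes the two arms comparable. Deleting subjects because of something that happens afterwards, and that is probably linked to pain, undoes that. Subjects in more pain tend to take more analgesia and subjects in less pain tend to take less, so those removed are likely to come from the ends of the outcome distribution.

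Three features of the wording make this worse.

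1. The rule has no direction. Subjects who reduce medication and subjects who escalate can both be dropped.
2. It does not match the endpoint sentence. That sentence sets no threshold, while the rule needs a *significant* change. A small increase fails the first and passes the second. Whether a reduction breaches the first is unclear.
3. The arm is unclear. The visit schedule in section 7.0 lists MRgFUS treatment and the sham procedure as alternatives, which points to the active arm only. Section 6.5, step 17, uses the MRgFUS term in steps common to both arms, which points to both.

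At stake is the only between-arm efficacy contrast in the study. Because subjects with a medication change stay in follow-up, the rule discards Month 3 scores that will have been collected.

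**Working it through.** **Inputs.** From the protocol: 10 subjects randomised 1:1, so about 5 per arm (section 8.4); a 2-point benchmark and a responder definition of 3 points or better (section 8.2). The protocol gives no SD of change, no rate of medication change and no efficacy calculation, so there is no figure to reproduce. The SDs, sham response and dropping rules below are assumptions.

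**1. Shift in one arm's mean.** If *k* of 5 subjects, each *d* points to the same side of the arm mean, are removed, the other 5 − *k* have a total deviation of −*kd*. The mean therefore moves by *kd*/(5 − *k*).

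| | d = 2 | d = 3 | d = 4 |
|---|---|---|---|
| k = 1 | 2/4 = 0.50 | 3/4 = 0.75 | 4/4 = 1.00 |
| k = 2 | 4/3 = 1.33 | 6/3 = 2.00 | 8/3 = 2.67 |

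The 2.00 case is demanding. The other three subjects must average 2 points on the other side, so the arm's SD is at least √((2×9 + 3×4)/4) = 2.74.

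**2. Expected shift if the most extreme subjects on one side are dropped.** For 5 normal values the two largest have expected values 1.163 and 0.495 SD. Dropping one gives 1.163/4 = 0.29 SD; dropping two gives (1.163 + 0.495)/3 = 0.55 SD. At SD 2, 2.5 and 3 this is 0.58, 0.73 and 0.87 points for one, and 1.10, 1.38 and 1.66 points for two.

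**3. Weaker or no dependence.** With 20% dropped, log-odds of being dropped rising by 1 per SD of outcome, and SD 2.5, the shift is 0.43 points. With no dependence it is 0.

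**4. Effect on the difference between arms.** Simulation with 1,000,000 subjects per arm; improvement normal, sham mean 1, SD 1.5 to 3. Worsening (change below 0) stands for escalation, and improvement of 4 points or more stands for reduction.

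| Subjects dropped | True difference 2, SD 2 | True difference 2, SD 1.5 to 3 | True difference 0, SD 1.5 to 3 |
|---|---|---|---|
| Worsened, both arms | 1.26 | 1.44 to 1.06 | about 0 |
| Strongly improved, both arms | 1.26 | 1.44 to 1.07 | about 0 |
| Worsened, active arm only | 2.28 | 2.08 to 2.86 | +0.64 to +1.79 |
| Strongly improved, active arm only | 0.98 | 1.36 to 0.20 | −0.08 to −0.87 |

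Applied alike to both arms, either rule shrinks a true effect and creates none under the null. Applied to the active arm only, it can inflate, shrink or invent a difference.

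**5. One made-up data set of the trial's size.** Sham improvements −1, 0, 1, 2, 3 (mean 1) and active 0, 1, 3, 5, 6 (mean 3) differ by 2.0. Dropping one subject gives:

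- worst active: 15/4 − 1 = 2.75
- best active: 9/4 − 1 = 1.25
- worst sham: 3 − 6/4 = 1.50
- best sham: 3 − 2/4 = 2.50

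So even under a both-arm rule, which subject happens to be dropped can move the estimate up or down.

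**6. Responders.** If 3 of 5 respond (60%), one deletion gives 2/4 (50%) or 3/4 (75%). Two deletions of the same kind give 1/3 (33%) or 3/3 (100%).

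**The case against.** The strongest reply is that little depends on this. Safety is the primary outcome and these subjects stay in it, and no test is planned. At an assumed SD of 2 the 95% half-width for the difference is already 2.9 points with 5 per arm, so a shift of 0.4 to 0.9 points lies well inside the noise. Criterion 9 should make changes uncommon. The largest distortions need the active-only reading, or two deletions on the same side of one arm. A statistical analysis plan, not seen here, could define *significant*, its direction and who judges it. Restricting to stable medication also answers a recognisable question, because added analgesia can lower NPRS and mask a difference. The simulation leaves that drug effect out, so in it keeping everyone must return the true value.

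Much of this limits the size of the problem. The illustrations are not predictions, the active-only reading is only one of two, and missing definitions alone would not be a protocol error. The core remains. The deletion is fixed in the protocol, and an analysis plan that follows it would still discard these subjects. Imprecision does not excuse a systematic shift, and a descriptive mean can mislead without a p-value. Criterion 9 covers prescribed doses while PRN use is recorded separately, and sections 6.7 and 8.2 both anticipate changes. Masking by analgesia is a reason to show the stable-medication subset beside the full comparison, not in place of it.

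**Conclusion.** The concern holds and should be fixed. Followed as written, section 8.2 can distort the study's own primary efficacy contrast. That the rule exists and acts after randomisation is certain from the text. The size of the bias is not, because it depends on an SD and a rate of medication change that the protocol does not give.

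On the assumptions above, an arm mean moves by about 0.4 points under moderate dependence, 0.6 to 0.9 if the single most extreme subject is lost, and 1.1 to 1.7 if the two most extreme on one side are lost. The expected shift is zero if medication changes are unrelated to pain. The expected direction is towards no difference if the rule acts alike in both arms. It can be either way if only the active arm is affected, or by chance in arms of five.

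**What to change.** Rewrite the efficacy paragraphs of section 8.2 as follows.

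- **Main summary:** all randomised subjects in their assigned arm, on observed worst NPRS at Month 3, regardless of medication change.
- **Medication table:** changes by arm and direction, with prescribed and PRN use shown separately.
- **Sensitivity analysis:** the stable-medication subset, with *significant* and its direction defined in advance and the same definition applied to both arms. The pain management specialist, already blinded under section 6.4, would classify changes from the medication record before the arm is disclosed.
- **Consistency:** make the endpoint qualifier and the medication rule describe the same condition, and state which arms it covers.

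The cost is wording, plus a small classification task for the specialist, whose scheduled examinations are at screening and Month 3 only. NPRS and medication use are already recorded at every follow-up visit, so no new visits, subjects or data are needed. The drawback is that the main estimate then includes any effect of medication change on pain: escalation could lower NPRS and narrow a difference. Showing the stable-medication subset alongside lets readers see this.

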8.3 Subject Health Status

The results from the physical and neurological exams will be recorded in the CRFs and will be analyzed.

8.4 Statistical Considerations and Sample Size

This is a feasibility study of ten (10) subjects who will be randomized in 1:1 fashion to receive either bilateral FUS medial thalamotomy or a sham procedure. A statistical analysis is not proposed. Nevertheless, reported adverse events will be examined and analyzed and used as a basis for determining the nature and extent of future studies.

8.5 Subject Confidentiality

Subject confidentiality will be maintained throughout this study, including all publications. Data collected and entered into the CRFs are the property of Insightec as the study sponsor. Representatives from the study sponsor or authorized sponsor representatives, the Institutional

Review Board Ethics Committee or other regulatory bodies may receive copies of the study records and may review medical records related to the study.

9.0 RISK MITIGATION

Worldwide, over 12,500 treatments have been performed to date with the MR guided FUS ExAblate body system. Risk analysis for InSightec ExAblate systems/clinical investigations has been conducted as part of previously approved FDA IDE submissions (G930140, G990151, G990184, G990201, G000203, G010225, G020001, G020182, G050177, and G060023, G070022, G080009, G080206). This data has been re-examined by InSightec and it has been concluded that this risk analysis has limited applicability to the proposed clinical investigation. The key consideration here is the fact that this proposed study is conducted with an ExAblate Neuro that is completely different from the body system. This system is referred to internally as the Exablate Neuro system. However, in principle, the body and brain systems have the same purpose namely to coagulate soft tissue within the body by means of MR guided high intensity focused ultrasound. The potential risks described below will be explained to the subject in the informed consent process.

9.1 General Device Related Risks

Risk of Magnetic Resonance Scanners:

MRI has no known deleterious biological effects in subjects with no contraindications. The incidence of claustrophobia during MRI examinations is approximately 10-15%, although it is expected to be less frequent in the study population due to the use of sedation.

Risk of Intravenous (IV) Catheter:

There is a potential risk from the IV catheter used during the ablation. Participants can expect a small amount of pain and/or bleeding/bruising at the IV site. There is a small risk of infection. This procedure will follow the ‘standard of care’ at the study sites.

Risks related to Dynamic FDG PET imaging:

PET Scan: This imaging study involves radiation exposure from a Positron Emission Tomography (PET) scan combined with a Computed Tomography (CT) scan using the radiopharmaceutical F-18 FDG. Using the standard way of describing radiation dose, from participating in this study, the wall of your bladder, heart, and pancreas will receive the most radiation from this study. All other organs will receive smaller amounts of radiation. Although each organ will receive a different dose, the total effective radiation dose you will receive from one procedure is approximately 10 mSv. You will have 2 of these scans. For comparison, this dose is roughly 40% the annual radiation dose safely allowed for a radiation worker such as the person performing your scan.

This radiation exposure is not necessary for your medical care but is necessary to obtain the research information desired. This radiation dose is what you will receive from this study only and does not include any exposure you may have received or will receive from other tests. If you

are pregnant or breastfeeding, you may not participate in this research study. It is best to avoid radiation exposure to unborn or nursing children since they are more sensitive to radiation than adults.

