3.2 Efficacy

Outcome assessments will primarily be made at baseline, one, and three months post procedure for patients receiving either the active treatment or sham procedure. Clinical assessments of pain will be made at all clinic visits.

Primary outcome: **safety** as assessed from adverse event reporting and MRI evaluation

Primary efficacy outcome measure will compare the change of **WORST** pain experienced in 24 hours before and at 3 months following bilateral FUS medial thalamotomy versus sham procedures as determined from the 11-point numeric pain rating scale.

Secondary outcome measures will include other patient-reported outcomes including the Global Impression of Change and the Pain Domain from the PROMIS Inventory including items for intensity, quality, behavior and interference.

Imaging assessments will be obtained before and after treatment. The location and precision of the treatment, as well as the volume of the lesion, will be determined from pre- and posttreatment MRI at baseline, 1 day, 1 week, 1 month and 3 months. Functional imaging assessments with Dynamic 2-[¹⁸F] fluoro-2-deoxy-D-glucose Positron Emission Tomography (FDG PET) will be obtained at baseline and three months for each patient. Functional imaging will serve as an objective measure to correlate with clinical pain assessment.

A summary of outcome measures is listed:

Primary (efficacy) outcome: 11-point numeric pain rating scale NPRS (“worst” NPRS score over 24 hours). The change in pain rating from baseline to 3 months posttreatment will be determined and compared between treatment and control cohorts.

Secondary outcomes:

Patient-reported outcome measures:

- PROMIS scale v1.0 – Pain Intensity 3a
- PROMIS scale v2.0 – Neuropathic Pain Quality 5a
- PROMIS scale v2.0 – Nocioceptive Pain Quality 5a
- PROMIS scale v1.0 – Pain Behavior 7a
- PROMIS scale v1.0 – Pain Interference 8a
- Patient Global Impression of Change, 7 point

Functional imaging assessments:

- Dynamic FDG PET

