4.1 The Hypotheses Tested

- For patients with treatment-refractory chronic trigeminal neuropathic pain, MR guided focused ultrasound can safely create lesions, bilaterally, in thalamic nuclei to reduce pain and provide functional benefits in daily activities.
- FUS under MRI-guidance and MRI-based thermometry can be safely delivered through an intact human skull with a low risk of transient adverse effects as evaluated during blinded follow-up of up to 3 months and an additional 3 months follow-up in open-label setting for those subjects who were initially randomized to Sham treatment.
- Pre-defined medial thalamic target volumes inside the brain can be precisely ablated, as demonstrated on post-treatment MRI.

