6.0 INVESTIGATIONAL PLAN

6.1 Study Design

This study is designed as a prospective, double-blinded, randomized trial in 10 subjects with sham procedures serving as the control. A rigorous clinical trial design is required for the subjective measurement of pain and clinical outcome where a placebo effect is anticipated. Primary safety and efficacy assessments will be made before and after treatment through the 3 month blinded phase. After 3 months, subjects in the sham arm will be offered a focused ultrasound bilateral thalamotomy as an open label extension of the study. All subjects receiving treatment, either during the primary blinded analysis or open-label extension phase, will be followed for at least 3 months post-thalamotomy.

Neuropathic Pain Study Flow

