6.2 Sham Study Design

The randomized, control arm subjects will undergo a sham procedure that is identical to the treatment except the energy output will be disabled. These control subjects will then be followed up for 3-months post-sham procedure to assess study endpoints; study follow-up: 1 day, 1 week, 1 and 3 month visits.

At the 3-Month time point, all subjects will be unblinded and offered crossover to the actual treatment. All these crossover subjects will be followed again according to the same schedule as the treatment through the Month 3 post treatment study visit.

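### Section 9.1 gives every subject two PET scans (about 20 mSv), but the crossover schedule as written gives a sham subject who completes crossover three (about 30 mSv)

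*Protocol*

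**What the plan says.** **Count and dose.** Section 9.1 says that "the total effective radiation dose you will receive from one procedure is approximately 10 mSv" and then "You will have 2 of these scans". It adds that "this dose is roughly 40% the annual radiation dose safely allowed for a radiation worker", without giving the allowance itself. The statement covers the whole study and does not separate the arms or mention crossover. Section 3.2 is consistent with it: dynamic FDG PET "will be obtained at baseline and three months for each patient".

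**Use of the text.** Section 9.0 introduces the risk sections with "The potential risks described below will be explained to the subject in the informed consent process".

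**Crossover.** Section 6.2 says: "All these crossover subjects will be followed again according to the same schedule as the treatment through the Month 3 post treatment study visit". Section 4.1 refers to "an additional 3 months follow-up in open-label setting for those subjects who were initially randomized to Sham treatment", and section 6.1 says: "All subjects receiving treatment, either during the primary blinded analysis or open-label extension phase, will be followed for at least 3 months post-thalamotomy". Footnote 1 of the section 7.0 schedule sets the re-entry point for sham subjects at Day 0.

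**Where the procedures sit.** PET is marked in the Baseline and Month 3 columns of the schedule and is listed under Month 3 in section 6.7.4. PT, PTT, the blood count with platelets and the Beta-hCG test appear only among the screening steps of section 6.3. The schedule marks screening labs only in the Screening column. The procedure-day steps in section 6.5 contain neither a coagulation nor a pregnancy test.

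**The concern.** Sections 9.1 and 3.2 give one PET count for everyone. Sections 6.2 and 6.7.4 and footnote 1, followed literally, give a different count for one group. Crossover is offered to every sham subject, so this group could be half the trial.

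The number at stake is a radiation dose that section 9.1 itself describes as serving research and not the subject's care, and that section 9.0 says will be explained at consent. If three scans are meant, the protocol understates the exposure of crossover subjects. If two are meant, the crossover schedule asks for a scan that nobody intended.

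The same re-entry rule has a second, smaller consequence. For a sham subject the crossover procedure is the first real thermal ablation, yet no scheduled test refreshes the results behind exclusions 17 (coagulation) and 20 (pregnancy) before it.

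**Working it through.** **Inputs**

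- Dose per PET procedure: about 10 mSv (9.1).
- Stated scans per subject: 2 (9.1).
- Stated share of a worker's annual allowance: roughly 40% (9.1).
- PET visits: Baseline and Month 3 (7.0; Month 3 also in 6.7.4).
- Crossover: re-entry at Day 0, then the same schedule through Month 3 (6.2; 7.0 footnote 1).
- Sample: 10 subjects, 1:1 (8.4).

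**Step 1. Reproduce the stated figure.** A subject who does not cross over has PET at Baseline and at Month 3.

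- Scans: 1 + 1 = 2, as stated.
- Dose: 2 × 10 = 20 mSv.
- Implied allowance, taking the 40% as covering both scans: 20 / 0.40 = 50 mSv.

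**Step 2. Count for a sham subject who completes crossover.** Re-entry at Day 0 comes after the Baseline column, so no new baseline PET is scheduled. The second Month 3 visit is repeated.

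| Visit | PET scheduled | Running dose |
|---|---|---|
| Baseline | yes | 10 mSv |
| Month 3 after sham | yes | 20 mSv |
| Month 3 after crossover thalamotomy | yes, no waiver | 30 mSv |

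- Dose: 3 × 10 = 30 mSv.
- Against the stated total: 30 / 20 = 1.5, or 10 mSv (50%) more.
- Against the implied allowance: 30 / 50 = 60%, compared with the stated 40%.

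**Step 3. Subjects affected.** At 1:1, 10 × 1/2 = 5 sham subjects. Between 0 and about 5 are affected, depending on how many complete crossover. Scans in the whole study: 10 × 2 = 20 as stated; 5 × 2 + 5 × 3 = 25 at most as scheduled.

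**Step 4. Age of the laboratory results at crossover.** Taking Month 3 as 13 weeks with its 14-day window, the earliest crossover is 13 − 2 = 11 weeks after the sham procedure. Screening comes before that procedure, so the results are at least about 11 weeks old. The original screening interval and any wait for the second procedure add to this. Coagulation or pregnancy tests scheduled between re-entry and the crossover ablation: 0.

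**The case against.** The strongest reply is that two scans were intended. Section 3.2 gives the timing of PET, assigns it at baseline and three months per patient, and agrees with 9.1. No sentence names a third scan; it follows only from general wording about repeating the schedule. This stands as far as intent goes, and it is why the point is an internal contradiction and not an arithmetic error: 2 × 10 mSv is correct for the path that 9.1 describes. It does not remove the need for a correction. If two is right, 6.2 and footnote 1 need an exemption. Section 3.2 also calls for imaging before and after treatment, and with two scans a crossover subject has no PET after the real ablation.

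Three stronger readings are tempting, and the documents do not support them:

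- **A reader might infer that three scans exceed the annual worker allowance**, by applying the 40% to a single scan (10 / 0.40 = 25 mSv; 30 / 25 = 120%). The percentage directly follows the statement that there are two scans, in a paragraph about the dose from taking part. The natural reading is therefore the two-scan total and an allowance of about 50 mSv.
- **A reader might infer that subjects are misinformed at consent.** The consent form is not available here, so whether it repeats the count is unknown.
- **A reader might infer that crossover subjects are ablated without bleeding or pregnancy safeguards.** Retesting is not forbidden. Contraception is required throughout the study (6.3), and antithrombotic exclusions are timed to treatment (5.3, item 12). The drug-stop reminder and medication review are procedure-day steps (6.5), and the investigator may withdraw a subject (9.10). No maximum age of results is set for the first procedure either, so the gap is not peculiar to crossover. These measures reduce the risk but do not replace the tests.

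**Conclusion.** The contradiction holds. As the schedule is written, a sham subject who completes crossover has 3 PET scans and about 30 mSv. Sections 9.1 and 3.2 give 2 scans and about 20 mSv to everyone. The difference is 10 mSv per affected subject, in up to about 5 of 10 subjects. The dose rises from about 40% to about 60% of the implied allowance.

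The 30 against 20 mSv comparison rests only on the protocol's per-scan dose and its schedule. The 60% also assumes that the 40% covers both scans, because the protocol states no allowance. The figure of 5 assumes an exact 1:1 split and that every sham subject completes crossover.

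The laboratory gap is secondary: a low-cost safety improvement, not evidence of harm. Neither issue touches the randomized comparison, which ends at the blinded Month 3 visit.

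**What to change.** **PET count: choose one.**

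1. In 9.1, state both paths: 2 scans and about 20 mSv in total for most subjects; 3 scans and about 30 mSv in total for those who receive sham first and complete crossover. Say that the 40% refers to the two-scan total, and align 3.2. Cost: a sentence or two, and a higher disclosed dose for crossover subjects.
2. In 6.2 and footnote 1, exempt the crossover Month 3 visit from PET. Cost: one sentence, and crossover subjects then have no post-ablation PET. Such scans would exist for about 5 subjects, where the repeated schedule would give up to 10.

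Whichever is chosen, the consent text should match it.

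**Secondary improvement.** Add to footnote 1 that PT/PTT/INR, platelets and, where applicable, Beta-hCG are repeated within 1 week before the crossover ablation. The schedule already uses a 1-week window for Baseline. Cost: one blood draw and, where applicable, one pregnancy test in up to about 5 subjects.
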